#### **1.4.2 Specific objective**

- (1) Evaluate the effects of static balance training, dynamic balance training, and combined static-dynamic balance training on the stability of beginner gymnasts. Quantify the maximum single-leg extension distance (reflecting lower limb support force) and the bilateral symmetry index (reflecting neuromuscular coordination) through the SEBT test to compare the differential effects of different training modes on stability improvement.
- (2) To evaluate the effects of static balance training, dynamic balance training, and combined static-dynamic balance training on the jumping skills of beginner gymnasts, this study measures the changes in data (such as jumping height, peak force, rate of force development, and impulse) of athletes during countermovement jump (CMJ) and single-leg countermovement jump (SLCMJ) before and after training. Through these measurements, it

aims to deeply analyze the mechanism of action of different training modes in enhancing the jumping ability of beginner gymnasts.

(3) This study aims to explore the improvement effects of static balance training, dynamic balance training, and combined static-dynamic balance training on the performance of gymnastic movements (such as standing 360° single-leg turn and straight jump 360° turn). Through three-dimensional motion capture technology, the study assesses beginner gymnasts in terms of center of gravity deviation distance, body oscillation amplitude, rotation smoothness index, and landing impact force during the standing 360° single-leg turn. For the straight jump 360° turn, it conducts quantitative analysis based on center of gravity deviation distance, joint angle variation, vertical jump efficiency, and landing impact force.

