## **1.6 Definitions of Operational Terms**

There operational terms used in this research proposal are shown below:

Static Balance:	The ability to regulate the body's center of gravity in a relatively stationary state (Halabchi et al., 2020).
Dynamic Balance:	The ability to regulate the body's center of gravity and adjust posture during movement (Lu et al., 2022).
Stability:	The inherent characteristic of an object to maintain or restore balance and avoid tipping over (Abadi Marand et al., 2023).
Human Stability:	The inherent ability of the human body, through the motor system, sensory system, and individual characteristics, to maintain, achieve, or restore balance and prevent falling (Thomas et al., 2019).
Jump or Leap in Gymnastics:	A skill in which athletes use lower body strength to propel themselves off the ground, perform specific movements or postures in the air, and land steadily (Suchomel et al., 2016).
Beginner Gymnasts:	Gymnasts with less than 1 year of systematic training experience in gymnastics, have not yet acquired complex gymnastic skills, and are in a phase of rapid development regarding fundamental physical fitness and motor skills. (Vickers, 1988).

Kinesiology in Gymnastics:	Kinesiology in gymnastics mainly describes the characteristics of athletes' movements (Al-Jaafreh & Qawaqzeh, 2024).
Definition of Biomechanics in Gymnastics:	Biomechanics in gymnastics combines biological and mechanical principles to study the laws of athletes' mechanical movements (Bartlett, 2014).
Peak Force:	During the concentric contraction phase (i.e., from the lowest point of the squat during the push-off until just before toe-off), the ground reaction force (GRF) gradually increases as the muscles generate force, and the highest force value within this phase is defined as the peak force (Kim et al., 2022).
Rate of Force Development:	The rate of force development (RFD) in countermovement jumps refers to the rate at which ground reaction force (GRF) changes over time during the concentric contraction phase (from the lowest squat point to just before takeoff) (Mackala et al., 2013), reflecting the neuromuscular system's ability to generate force rapidly and directly determining explosive takeoff power (Djurić et al., 2023).

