In gymnastics, stability during the jumping and landing phases is of utmost importance. Landing stability reflects the body's ability to absorb impact forces and maintain balance, with key test metrics including: Landing Impact Force (N), which measures the ground reaction force (GRF) at the moment of landing and directly demonstrates an athlete's capacity to absorb impact forces (Seegmiller & McCaw, 2003); Center of Mass Displacement, which evaluates the movement of the center of gravity (COG) during landing—the smaller the displacement, the higher the stability (Dingenen et al., 2016); Landing Time (s), which refers to the time required for the body to stabilize after touching the ground and reflects the athlete's recovery speed (Nazari & Hooi, 2019); and Postural Control, which uses 3D motion capture or video analysis techniques to assess the stability and coordination of various body parts during landing (Müller et al., 2017).

Stability testing also includes dynamic balance assessments, such as the 8 - Point Star Offset Test. This test mainly evaluates the athlete's dynamic balance and adaptability in multiple directions, especially in complex and multi - task environments (Yoon et al., 2020). By incorporating these metrics into the stability assessment system, a comprehensive and in - depth analysis of gymnasts' performance can be achieved, providing valuable references for improving execution accuracy, reducing the risk of injury, and optimizing training programs (Daly et al., 2001).

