### **3.8.2 Research tool**

#### **3.8.2.1 Kunwei Force Plate (jumping test)**

The Kunwei force plate is a high-precision biomechanical measurement device widely used to assess jump performance, balance, and force development in athletes (Cormie et al., 2007). To scientifically evaluate the biomechanical performance of the countermovement jump (CMJ) and single-leg countermovement jump (SLCMJ), the standardized testing protocol using the

Kunwei Force Plate is as follows: Participants stand barefoot on the force plate with arms relaxed to complete a 10-second static calibration, recording baseline center of pressure (CoP) trajectories (re-test required if CoP drift exceeds 2 cm), with the system sampling rate set to 1000 Hz. For CMJ testing, participants perform rapid countermovement jumps from self-selected knee flexion depth to maximal height, landing symmetrically and stabilizing for 2 seconds, repeated 5 times (60-second rest intervals) (Markovic et al., 2004). For SLCMJ, participants execute single-leg jumps followed by ipsilateral landing with 3-second balance maintenance; failed trials (contralateral limb contact or external support) trigger retesting. The force plate continuously acquires vertical ground reaction force (vGRF) to calculate jump height (flight time method:  $h = \frac{g \times t^2}{8}$  ) peak force (max vGRF), rate of force development (RFD: slope of force-time curve from 0-200 ms), and impulse (force-time integral). Real-time feedback on adjacent screens highlights critical metrics (e.g., RFD < 3000 N/s—optimize ankle stiffness or bilateral peak force asymmetry > 10%—adjust symmetry). Raw data undergo Butterworth low-pass filtering (50 Hz cutoff) and body weight normalization, with outliers excluded based on predefined criteria (e.g., pre-activation force exceeding 5% body weight or stabilization time > 1.5 seconds). Processed datasets are encrypted and stored as CMJ/SLCMJ-Date-Subject. This protocol quantifies lower-limb explosive power, bilateral symmetry, and energy transfer efficiency (Gathercole et al., 2015), supporting athlete selection, training monitoring, and rehabilitation assessment (Meylan & Malatesta, 2009).

Figure 11 Kunwei Force Plate

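### Jumps are excluded when landing stabilisation exceeds 1.5 s, so take-off and flight outcomes are selected on a balance ability that the training targets

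*Protocol*

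**What the plan says.** Section 3.8.2.1 (Kunwei Force Plate) sets one outlier rule for the CMJ and SLCMJ recordings: "outliers excluded based on predefined criteria (e.g., pre-activation force exceeding 5% body weight or stabilization time > 1.5 seconds".

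The section does not define stabilisation time, but the only stabilising actions in the jump procedure come after landing. For the CMJ the task is "landing symmetrically and stabilizing for 2 seconds, repeated 5 times"; for the SLCMJ it is "ipsilateral landing with 3-second balance maintenance". Section 2.6 lists a corresponding landing-stability measure: "Landing Time (s), which refers to the time required for the body to stabilize after touching the ground".

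Repeat jumps are provided for in one situation, stated for the SLCMJ: "failed trials (contralateral limb contact or external support) trigger retesting". Slow stabilisation is not among those triggers.

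The outcomes for the second objective (section 1.4.2) are changes in data "such as jumping height, peak force, rate of force development, and impulse", and Table 17 reports these four. Section 1.6 places peak force in the concentric phase before toe-off: "the highest force value within this phase is defined as the peak force". It places RFD in the same phase and ties net impulse to take-off velocity and jump height. Section 3.8.2.1 computes jump height from flight time; section 3.2.2.2 uses impulse-momentum up to take-off.

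**The concern.** A validity rule should remove recordings that do not measure what they are meant to measure. Pre-activation above 5% body weight is such a fault, because it disturbs the force baseline before the jump. Slow balance recovery is different. It is a performance result that arises after the quantities of interest have been determined.

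The rule would be merely wasteful if slow recovery were unrelated to treatment. Here it may be related. Section 1.2 names the moment of landing after a jump as a focus of dynamic balance training. Landing control drills appear in the dynamic programme (Table 14, week 7) and the combined programme (Table 15, weeks 4 and 7), while the control group keeps its routine training. Different fractions of otherwise usable jumps may then be removed by arm, and from baseline to week 8. That is selection after randomisation, acting directly on the group-by-time comparison in Table 17.

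**Working it through.** The plan gives no figure for this rule, so there is none to reproduce. The check is a reading of when each outcome is fixed, followed by an illustration of size.

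**1. When is each outcome fixed?**

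| Outcome | Source | Fixed by |
|---|---|---|
| Peak force | 1.6, concentric phase | before take-off |
| RFD | 1.6, concentric phase; 3.8.2.1, slope over 0–200 ms | before take-off |
| Net impulse | 1.6, determines take-off velocity | take-off |
| Jump height | 3.2.2.2, impulse-momentum | take-off |
| Jump height | 3.8.2.1, h = g·t²/8 with t = flight time | touchdown |

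None depends on how long balance takes after touchdown.

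**2. Is an excluded jump replaced?** No replacement is stated for the stabilisation ground. The calculation below assumes none.

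**3. How large could the effect be?** The documents give no distribution of stabilisation times, so every input here is an assumption except the 1.5 s limit and the five jumps.

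- Stabilisation time is normal with SD 0.4 s and control mean 1.1, 1.3 or 1.5 s; training shortens it by 0.3 s.
- Half the variance is between participants and half between jumps.
- The correlation r between height and stabilisation time is −0.3, 0 or +0.3.
- Training has no true effect on jump height.

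Share excluded = 1 − Φ((1.5 − mean)/0.4). For a control mean of 1.1 s this is 1 − Φ(1.00) = 16%, against 1 − Φ(1.75) = 4% for a trained mean of 0.8 s. The other rows follow in the same way. The shares losing all five jumps and the height differences come from simulation (200,000 participants per arm and scenario). Differences are trained minus control, in SD of a single jump's height.

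| Control mean | Excluded, control vs trained | All five lost, control vs trained | Mean height, r = −0.3 / 0 / +0.3 | Best jump, r = −0.3 / 0 / +0.3 |
|---|---|---|---|---|
| 1.1 s | 16% vs 4% | 1.5% vs 0.1% | −0.04 / 0.00 / +0.05 | +0.03 / +0.07 / +0.12 |
| 1.3 s | 31% vs 11% | 6% vs 0.7% | −0.08 / −0.01 / +0.08 | +0.05 / +0.13 / +0.21 |
| 1.5 s | 50% vs 23% | 17% vs 3% | −0.12 / 0.00 / +0.12 | +0.06 / +0.17 / +0.30 |

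The last row can be checked by hand. The mean height of retained jumps shifts by −r·φ(z)/Φ(z). For controls z = 0, so φ/Φ = 0.399/0.500 = 0.798. For trained participants z = (1.5 − 1.2)/0.4 = 0.75, so φ/Φ = 0.301/0.773 = 0.389. With r = 0.3 the difference is 0.3 × (0.798 − 0.389) = 0.12, as simulated.

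The best-jump column is positive even at r = 0 because the control arm keeps fewer jumps from which to take a maximum.

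**4. After the change.** If these outcomes are kept whatever the stabilisation time, this criterion removes 0% of jumps in every arm and the selection difference is 0.

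**The case against.** **Landing is not irrelevant to the recorded outcomes.** Flight time ends at touchdown, so landing posture enters flight-time height, and section 1.6 does not define jump height. Section 3.8.2.1 also gives peak force as the maximum vertical force and impulse as a force-time integral without limiting the phase. This stands, and rules out saying that all four outcomes are complete before landing. It does not rescue the rule. Posture at the instant of contact is not the time later spent regaining balance, and the missing phase limit is cured by applying section 1.6.

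**The direction is unknown.** A reader might infer that higher jumps are harder to stabilise, so that the rule creates an apparent jump gain in trained arms. The documents do not say so. If better jumpers also land better, the correlation is negative and the bias in mean height reverses.

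**The size is assumed and modest.** The participants are injury-free physical-education students, so exclusions could be rare. The planned effect size f = 0.35 implies at least 2 × 0.35 = 0.70 SD between extreme groups, well above 0.12. This stands as a limit on severity.

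**The rule is loosely worded.** It is introduced as an example, stabilisation time is undefined, and the unit dropped is not stated. A reader might infer that participants leave the HA2 analysis, but the text does not establish that. Such details may sit in a statistical analysis plan. The criterion is nonetheless named as predefined, so staff following the Protocol would apply it.

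**A landing measure is mentioned.** Section 3.2.2.2 includes force attenuation in the first 200 ms of landing, for which a landing criterion would be less out of place. Table 17 does not report it.

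**Conclusion.** The concern holds in a limited form. Section 3.8.2.1 makes inclusion of jump data depend on a post-landing balance measure that does not bear on the validity of the four analysed outcomes and that the training may change. Exclusion may therefore differ by arm and visit, with no stated replacement.

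This rests on reading stabilisation time as time after landing, the only sensible reading in that section. Under the stated assumptions the spurious difference in mean height is about 0 without correlation and −0.12 to +0.12 SD at correlations of −0.3 to +0.3. If the best jump is analysed it is +0.03 to +0.30 SD; section 3.8.2.1 does not say how the five jumps are combined. The documents determine neither sign nor size, and do not support a claim that the rule inflates the training effect. It is worth correcting because it discards usable data selectively and is easily removed before testing begins.

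**What to change.** In section 3.8.2.1:

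- Delete stabilisation time above 1.5 s as an exclusion for jump height, peak force, RFD and impulse.
- Keep exclusions for faults that corrupt the record itself: unstable weighing, pre-activation above 5% body weight, and landing off the plate so that flight time cannot be read. The last can also depend on balance, but there the measurement is truly missing.
- Apply the concentric-phase definition of section 1.6 to peak force, so that landing force cannot enter.
- Report stabilisation time, and the number of excluded or retested jumps, by arm and visit. This also shows whether the remaining exclusions and the SLCMJ retests differ between arms.

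The cost is a few phrases in one section and a short table, with no extra testing. The downside is that a few jumps with untidy landings are retained, adding slight noise to flight-time height.

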### **3.8.2.2 Star Excursion Balance Test, (SEBT) stability test**

The Star Excursion Balance Test (SEBT) is an effective tool for assessing dynamic balance in participants. During the test, the participant stands on one leg at the center of a star-shaped diagram and extends the other leg as far as possible in eight specific directions: anterior (ANT), anterolateral, lateral (LAT), posterolateral (PLAT), posterior (POST), posteromedial (PMED), medial (MED), and anteromedial (AMED) (Dendrinos et al., 2022). These directions are designed to evaluate balance in multiple planes. The maximum reach distance in each direction, normalized to the participant's leg length, is used as an indicator of dynamic balance ability. Before the formal test, participants should undergo adequate practice trials to ensure proficiency and reliable data. During the test, the standing leg must remain stable, and the participant should avoid significant shifts in the center of gravity or loss of balance. Each direction should be tested multiple times, and the average of the best scores is used for analysis. Studies have shown that SEBT is highly sensitive in detecting functional deficits in the lower limbs, making it particularly useful for evaluating dynamic balance in athletes. Additionally, SEBT can be used to assess the impact of core strength training on dynamic balance. Research indicates that athletes who undergo core strength

training exhibit significant improvements in SEBT performance, demonstrating that core training can enhance dynamic balance (Gong et al., 2023).

[figure not shown]

Figure 12 The Star Excursion Balance Test

### 3.8.2.3 TecnoBody 3D Motion Capture System (gymnastic performance movements)

To accurately assess the biomechanical parameters of the 360° straight jump turn and single-leg standing rotation, experimental procedures must integrate standardized protocols with real-time interaction: Test operators first instruct participants to stand still while reflective markers are affixed to anatomical landmarks (acromion, anterior superior iliac spine, greater trochanter, and lower limb joints), emphasizing that "markers must align with bone structures—avoid movement to prevent displacement (Soylu et al., 2025). During static calibration, participants are directed to stand naturally at the center of the force platform with arms relaxed and gaze forward, maintaining stillness for 10 seconds to establish the skeletal model. For formal testing, the straight jump turn requires execution under the command jump vertically, complete a 360° mid-air rotation, and land stably, while the single-leg rotation emphasizes upright posture on the support leg, stable trunk alignment, and 2-second balance maintenance post-rotation, with each movement repeated three times to ensure data reliability. During acquisition, the system provides real-time alerts such as "right knee marker

occluded—adjust arm posture and retest" or "insufficient rotational angular velocity—reduce trunk compensation," ensuring movement standardization. Coaches view screens displaying the participant's center of mass trajectory (red) overlaid with the ideal biomechanical model (green), accompanied by feedback like "0.2-second delay in hip extension—optimize takeoff sequencing." Post-test, data undergoes quality control screening (e.g., center-of-mass deviation standard deviation  $<1.5$  cm, marker occlusion rate  $<5\%$ ), encrypted and stored under the naming convention 'action-date' for subsequent biomechanical modeling and training optimization. This protocol, combining movement standardization, real-time correction, and multimodal data integration, enables granular analysis of rotational techniques (Bravi et al., 2023), supporting technical refinement and injury prevention research in disciplines such as artistic gymnastics and dance.

Figure 13(a) The 3D Motion Capture System

[figure not shown]

Figure 13(b) The Schematic placements of the motion capture system

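### Technique feedback triggered by poor performance is part of the jump and turn outcome tests, and nothing keeps it out of the scored trials

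*Protocol*

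**What the plan says.** Section 3.8.2.3 covers the straight jump 360° turn and the single-leg 360° turn. It opens by requiring that "experimental procedures must integrate standardized protocols with real-time interaction". After the formal test, "with each movement repeated three times to ensure data reliability", it continues: "During acquisition, the system provides real-time alerts such as" two examples. One concerns an occluded marker. The other is "insufficient rotational angular velocity—reduce trunk compensation". Coaches watch the participant's centre-of-mass path "overlaid with the ideal biomechanical model (green), accompanied by feedback like" a remark on late hip extension and how to improve the takeoff. The section sums up: "This protocol, combining movement standardization, real-time correction, and multimodal data integration".

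Section 3.8.2.1 sets out the force-plate procedure for the countermovement jump (CMJ) and its single-leg form (SLCMJ). "Real-time feedback on adjacent screens highlights critical metrics", and the examples pair a trigger with an instruction: RFD below 3000 N/s calls for better ankle stiffness, and peak-force asymmetry above 10% calls for a symmetry correction. CMJs are done five times with 60 seconds between them. No number of repetitions is given for the SLCMJ.

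Tables 9 and 10 (section 3.2.1.2) schedule these tests at baseline and week 8.

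**The concern.** An outcome test should meet each participant under the same conditions. Here the test conditions can depend on how well the participant performs. A cue given after one trial can change the next scored trial, and those who perform worse trigger more cues.

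An effect of cueing that was equal in all arms would cancel between arms. One triggered by poor performance need not cancel, because the less improved arm is cued more often at week 8. The hypotheses in section 1.5 are worded as improvement after training, and there a poorer baseline draws more help than an improved week-8 performance. Either way, the means planned for Tables 17, 19 and 20 could combine trained ability with coaching received on the test day. The protocol does not ask for cues to be logged, so the two could not be separated afterwards.

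**Working it through.** **1. Do the cues act on outcomes?**

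| Trigger or display | Section | Related outcome |
|---|---|---|
| RFD below 3000 N/s | 3.8.2.1 | RFD, Table 17 |
| Peak-force asymmetry above 10% | 3.8.2.1 | Peak force, Table 17 |
| Low angular velocity | 3.8.2.3 | Rotation smoothness index, computed from angular velocity (3.2.3.3.3), Table 20 |
| Late hip extension at takeoff | 3.8.2.3 | Straight jump turn outcomes, Table 19 |
| Centre-of-mass path against an ideal path | 3.8.2.3 | Centre of gravity deviation (3.2.3.2.1, 3.2.3.3.1), Tables 19 and 20 |
| Marker occlusion | 3.8.2.3 | None; a technical alert |

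All but the last respond to performance.

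**2. Is the feedback kept away from scored trials?** No section says so. The Star Excursion Balance Test is a useful contrast: section 3.8.2.2 puts practice trials before the formal test and describes no feedback. The point therefore covers the jump and turn tests only.

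**3. How large could the effect be?** The protocol gives no cue effect, standard deviation or cueing rate, so this is an illustration. All its inputs are assumptions except the five trials, which are the CMJ count.

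- The score of participant i on trial j is μ + b + e + c × (1 if an earlier trial fell below the trigger, otherwise 0).
- The total trial SD is 1 and the intraclass correlation 0.5, so b and e each have variance 0.5.
- μ is 0 untrained and 0.5 trained.
- The mean of five trials is analysed, and a cue's gain c lasts for all later trials.
- The trigger is the untrained 25th percentile or median.
- 200,000 participants were simulated per arm (Monte Carlo error about 0.003).

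Without cueing, the SD of the five-trial mean is √(0.5 + 0.5/5) = 0.775, and the standardised difference is 0.5/0.775 = 0.645. The simulation agrees (0.649 and 0.645 in the two runs).

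| Trigger | Cued before last trial, untrained vs trained | Mean difference, c = 0 / 0.2 / 0.4 | Standardised difference, c = 0 / 0.2 / 0.4 |
|---|---|---|---|
| 25th percentile | 52% vs 30% | 0.503 / 0.468 / 0.442 | 0.649 / 0.641 / 0.641 |
| Median | 80% vs 60% | 0.500 / 0.470 / 0.436 | 0.645 / 0.647 / 0.639 |

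Rounded, the mean difference goes from 0.50 to 0.47 or 0.44. That is 0.03/0.50 = 6% and 0.06/0.50 = 12%. With three trials, as for the turns, and the median trigger it is 0.502 / 0.476 / 0.446.

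The standardised difference hardly moves because cueing lifts low scorers and so narrows the spread. For the 25th-percentile trigger the implied SD falls from 0.503/0.649 = 0.775 to 0.442/0.641 = 0.690.

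**4. Against the trial's precision.** With 15 per arm (section 3.6), the standard error of a two-arm difference is 0.775 × √(2/15) = 0.283. The shifts of 0.03 and 0.06 are about 11% and 21% of that.

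**The case against.** **Delivery is inferred.** A reader might conclude that the protocol has participants coached between scored trials. It does not say that. Section 3.8.2.3 names coaches as viewers of the overlay, section 3.8.2.1 names no viewer, and the only example that orders a retest is marker occlusion. Both sections also drift into general device use, such as athlete selection and training optimisation, so some cues may be advice for later training. This stands as a limit on the claim. It does not remove it: interaction and correction in real time mean little if nothing reaches the participant, and no sentence excludes it.

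**One cue may enforce the task.** Section 3.2.3.3 requires constant speed and no trunk deviation, so the angular-velocity alert could be a compliance check. That is fair, but the same scripted instruction for everyone would do this without depending on performance.

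**The effect is small.** In the illustration it is, and it is toward the null. Randomisation balances baseline cueing in expectation. The real RFD trigger is fixed at 3000 N/s, so if nearly all or almost none of these beginners cross it, cueing would hardly differ by arm. The protocol does not say that the mean of five jumps is scored, and five repetitions should not be read across to the SLCMJ. All of this stands.

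**Sway.** Section 3.2.3.3 also makes a single-leg turn invalid if sway occurs, with no threshold, while body oscillation is an outcome (3.2.3.3.2, Table 20). A reader might infer that trials are selected on the outcome itself. The rule is judged on return to the starting posture and the outcome is measured during rotation, so the two are related but not the same. No repeat rule for invalid turns is stated, so no size is given.

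**Conclusion.** The point holds in a limited form. Performance-triggered technique feedback is described within the CMJ, SLCMJ and 360° turn outcome tests, and no text separates it from the scored trials. Followed as written, baseline and week-8 scores can mix same-day coaching with the training effect, both before against after and between arms.

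Its real size cannot be derived from the protocol. Under the assumptions above (ICC 0.5, true benefit 0.5 trial SD, cue effect 0.2 to 0.4 SD, mean of five trials) the mean difference shrinks by about 6 to 12% and the standardised difference by about 1%.

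A reader might infer a serious loss of power, for example by cutting the planning effect size of 0.35 by a similar percentage. The illustration does not support that, because the effect size used for power is standardised and barely changes. The case rests on what the scores mean, and on a very cheap remedy for something that cannot be corrected after the data are collected. It should be fixed. The sway wording is minor and optional.

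**What to change.** State in sections 3.8.2.1 and 3.8.2.3 that during scored baseline and week-8 trials no performance feedback and no coach's technique cue reaches the participant until testing ends. Keep technical alerts such as marker occlusion and calibration. Give every participant the same scripted task instruction. Performance displays can be shown once the last scored trial is done.

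Optional: in section 3.2.3.3, remove sway from the validity rule or define it as an end-posture failure.

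The cost is wording in the test procedure and a display setting, with no added staff, equipment or participants. The downside is slightly more variable trials. Section 5.2 dates data collection from 1/9/2026, after this version of 25/9/25, so on that timetable the change can be made before the first test.
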